### **3. Objectives**

The specific objectives addressed by the study are:

1. Is there an association between in-hospital mortality, 30-day mortality, and hospital length of stay and red blood cell transfusion at various levels of nadir haemoglobin?
2. Is there an effect modification between levels of nadir haemoglobin and presence of a red blood cell transfusion on in-hospital mortality, 30-day mortality, and length of stay?

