## **6.2. Description of data gathering methods, including definitions of variables.**

The majority of data needed for this project will be sourced from the *Western Australian Patient Blood Management System*. The advantages of sourcing the majority of data from one system include consistent data collection processes and classification of variables.

The exposure variables of interest are degree of anaemia and red blood cell transfusion. Anaemia will be defined using the nadir haemoglobin result during admission for those not transfused and the pre-transfusion haemoglobin result in patients transfused, as described previously. The pre-transfusion haemoglobin will be the closest level measured prior to the first red blood cell transfusion administered. Fridges are available for storing blood in theatres and because of this the timing of red blood cell transfusion in the operating room is unknown. Therefore for patients transfused in the operating room the nadir haemoglobin result will be used as a surrogate for the pre-transfusion haemoglobin result. Haemoglobin levels will be grouped into the following categories: below 50 g/L, 50-59 g/L, 60-69 g/L, 70-79 g/L, 80-89 g/L, 90-99 g/L, 100 g/L or over. These cutoffs were selected after reviewing similar studies.

The main outcome variables of interest are mortality and hospital length of stay of current admission. For the mortality analysis, both in-hospital and 30-day all-cause mortality will be assessed. In-hospital and 30-day mortality will be calculated from date of death recorded in hospital patient admission systems (TOPAS/WebPas). Potential confounders collected will include age at admission, sex, hospital, discharge year, admission type (emergency or elective), clinical specialty, and patient comorbidities.

Patient comorbidities will be assigned a score based on the Charlson Comorbidity Index derived from ICD-10 codes for the comorbidities identified. To ensure the Charlson score represents patient comorbidities on admission, hospital-acquired complications will be excluded from the calculation.

Other data items to be collected include admission date, discharge date, discharge specialty, diagnosis related group, hours in ICU, presence of a red blood cell transfusion (yes/no), had a massive transfusion (yes/no), and number of red blood cell units transfused.

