### **6.4. Statistical methods.**

Exposure and outcome variables will initially be described by univariate and bivariate statistics, the latter using the chi-squared test for categorical variables and independent samples t-test for continuous variables. Logistic regression models will be applied to test the relationship that both red blood cell transfusion and nadir haemoglobin levels have with in-hospital mortality and 30-day mortality. A zero-truncated negative binomial regression model will be applied to the length of stay outcome. All regression models will adjust for the same potential confounders. A robust variance adjustment will be applied to the regression models to account for any potential correlation between multiple admissions for the same patient.

For this analysis we are also interested in whether the presence of a red blood cell transfusion modifies the effect of nadir haemoglobin on in-hospital mortality, 30-day mortality and length of stay. To test any effect modification on outcome an interaction term between nadir haemoglobin level and red blood cell transfusion will be added to the multivariable logistic regression models. Only significant interactions (defined as p-values <0.05) will be reported, with calculated odds ratios for interaction terms presented.

In addition, Kaplan-Meier curves and Cox proportional hazards models will be plotted to show time to death in patients transfused red blood cells when compared to patients not transfused red blood cells across the various nadir haemoglobin levels.

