## 6.5. Sample size estimation.

Given the inclusion and exclusion criteria, there are expected to be between 60,000-70,000 consecutive inpatient admissions in the study cohort.

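### The p<0.05 rule for effect modification is not tied to one test: read coefficient by coefficient over seven haemoglobin bands, it exceeds 5% false positives for each mortality outcome

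*Protocol*

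**What the plan says.** Protocol section 3 sets the second objective: "Is there an effect modification between levels of nadir haemoglobin and presence of a red blood cell transfusion", for in-hospital mortality, 30-day mortality and length of stay. That is one null hypothesis per outcome.

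Protocol section 6.2 makes haemoglobin categorical, with these bands: "below 50 g/L, 50-59 g/L, 60-69 g/L, 70-79 g/L, 80-89 g/L, 90-99 g/L, 100 g/L or over". Transfusion is recorded as yes or no.

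Protocol section 6.4 says that "an interaction term between nadir haemoglobin level and red blood cell transfusion will be added to the multivariable logistic regression models", and then gives the decision and reporting rule: "Only significant interactions (defined as p-values <0.05) will be reported, with calculated odds ratios for interaction terms presented".

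The protocol names no joint test, trend test, reference band or multiplicity adjustment. Section 6.5 gives only an expected number of admissions ("there are expected to be between 60,000-70,000 consecutive inpatient admissions in the study cohort"), with no event rate and no distribution over the bands.

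**The concern.** Seven bands crossed with a binary exposure give 7 - 1 = 6 interaction coefficients. Each coefficient's p-value tests only whether one band's transfusion odds ratio equals that of the reference band. The objective's null is that all seven odds ratios are equal. If any coefficient below 0.05 counts as effect modification, that null is tested six times at 5%.

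The stake is practical. Section 4 hopes that the results will inform the thresholds chosen for future randomised trials. A single band that reaches p<0.05 by chance, shown while its non-significant neighbours are not, looks like such a threshold.

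The other natural reading, a joint test of all six coefficients, holds the 5% level. It ignores the order of the bands, however, so it is a weak instrument if the transfusion odds ratio really changes steadily with haemoglobin.

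**Working it through.** The protocol states no error rate or power for the interaction, so there is no figure of its own to reproduce. The inputs from the protocol are the threshold of 0.05 (two-sided assumed), seven bands, a binary exposure and 60,000-70,000 admissions (65,000 used). Everything else is an assumption.

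**1. False positives, term by term.** If the six tests were independent, the rate would be 1 - 0.95^6 = 26.5%. They share a reference band, so they are correlated. Let V be the variance of a band's log odds ratio for transfusion. The correlation of terms j and k is V_ref / sqrt[(V_ref + V_j)(V_ref + V_k)]. With a common correlation rho, Monte Carlo gives P(any of six |z| > 1.96) as follows:

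| rho | 0 | 0.3 | 0.5 | 0.7 | 0.8 | 0.9 | 0.95 |
|---|---|---|---|---|---|---|---|
| any of six | 26.5% | 24.1% | 20.8% | 16.4% | 13.9% | 10.8% | 8.9% |

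**2. The same under assumed cell counts.** Three splits of 65,000 admissions were tried. Each entry is share of admissions / share transfused / mortality, in percent, with mortality the same in both exposure groups (no effect modification).

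| Band (g/L) | A | B | C |
|---|---|---|---|
| <50 | 0.08 / 85 / 12 | 0.15 / 70 / 15 | 0.10 / 90 / 10 |
| 50-59 | 0.3 / 80 / 8 | 0.5 / 70 / 8 | 0.4 / 85 / 6 |
| 60-69 | 1.2 / 75 / 5 | 2 / 65 / 5 | 1.5 / 80 / 4 |
| 70-79 | 4 / 50 / 4 | 7 / 40 / 3 | 5 / 50 / 3 |
| 80-89 | 8 / 20 / 2.5 | 12 / 12 / 2 | 10 / 15 / 2 |
| 90-99 | 14 / 6 / 1.5 | 18 / 4 / 1.2 | 16 / 5 / 1.5 |
| 100 or over | rest / 1 / 0.7 | rest / 0.4 / 0.6 | rest / 2 / 1.0 |

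For a band with n admissions, transfused share t and mortality m, V = 1/[n t m(1-m)] + 1/[n(1-t) m(1-m)]. Example, split A, 100 g/L or over: n = 47,073, so V = 1/3.27 + 1/323.9 = 0.309; about 3.3 expected transfused deaths set the precision of all six terms.

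| Reference band | A | B | C |
|---|---|---|---|
| 100 or over | 18.2% | 11.5% | 22.3% |
| 70-79 | 25.5% | 25.7% | 25.4% |
| <50 | 11.0% | 16.2% | 10.0% |

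A separate patient-level simulation (65,000 admissions, about 700 deaths, 24 covariate strata, robust Wald tests, 32 untransfused admissions below 50 g/L) gave 14-16% for any term, 3-5% for the joint test and 4-6% for a 1-df trend. In sparser settings, among runs without a zero-death cell, the any-term rate was 12%.

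**3. Power of the joint test against a steady gradient.** If the interaction is exactly linear in the band score, both tests have the same noncentrality L and differ only in degrees of freedom.

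| L | 1-df trend | 6-df joint | Loss |
|---|---|---|---|
| 7.849 | 80% | 52% | 28 points |
| 10.507 | 90% | 67% | 23 points |
| 13 | 95% | 78% | 17 points |

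The loss peaks at about 29 points and falls to about 11 when the trend test has 98% power. In the patient-level simulation, with the odds ratio falling from 2.0 at the top band to 0.75 at the bottom, power was 34% joint and 55% trend; from 2.5 to 0.65 it was 60% and 81%. With only 10 untransfused admissions below 50 g/L (Firth joint test) it was 26% against 38%, and 44% against 61%, losses of 12 and 17 points.

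**4. The reverse case.** With noncentrality fixed at 7.849 (joint power 52%), the trend test keeps only the fraction r² of it, where r is the precision-weighted correlation between band score and true pattern. Over splits A to C, trend power was:
- step below 70 g/L: 40-59%;
- quadratic pattern: 9-47%;
- effect confined to the band below 50 g/L: r² = 0.10, 0.23 and 0.07, so 14%, 27% and 11%.

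**The case against.** The strongest reply is that section 6.4 speaks of one interaction term in the singular when the model is described, which fits a single overall test. Listing an odds ratio for each term is ordinary display after such a test, and a statistical analysis plan that is not shown may settle the matter. This stands in part. A reader might infer that the protocol commits to six separate tests; it does not say so. But it does state the decision rule and its threshold, in the plural for interactions, p-values and terms, and that rule permits the coefficient-by-coefficient reading. The defect is in a rule the protocol itself fixes, not in detail left for later.

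A reader might also add the two penalties together. They belong to alternative readings: the term-by-term rule inflates error, while the joint test holds 5% and is a valid test of the objective.

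Finally, a reader might conclude that a linear trend should replace the joint test because the protocol motivates a graded interaction. Sections 2 and 5 do report odds of death rising with each 10 g/L fall in haemoglobin, but in patients who were not transfused. That is a main effect of haemoglobin; the protocol itself notes that those studies are silent on the effect of transfusion. They also report a sharper rise below 50 g/L, and the interest in thresholds near 70 g/L suggests a step as readily as a line. Step 4 of the working shows what a trend test would give up in such cases.

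**Conclusion.** The concern holds as a defect of specification. Section 6.4 sets a significance rule for effect modification without tying it to one test of the Objective 2 null. Followed term by term, the false-positive rate per mortality outcome is roughly 9-26% instead of 5%, and about 12-22% under the assumed splits if 100 g/L or over is the reference. Followed as a joint 6-df test, the level is right, and the cost is roughly 10-30 points of power if, and only if, the interaction is a steady gradient.

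The inflation appears under every correlation and split tried; its size depends on a reference band, band sizes, transfusion shares and event rates that the protocol does not give. The calculations in steps 1, 2 and 4 are large-sample approximations, rough where a cell expects about one death. All figures concern the logistic mortality models; length of stay was not examined.

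**What to change.** In section 6.4:

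1. State that effect modification is judged, for each outcome, by one global test of all six interaction coefficients (joint 6-df), and not by individual coefficients.
2. Name the reference band.
3. Add a pre-specified 1-df trend interaction (transfusion by ordered band score, with the band main effects kept categorical) as a complementary analysis. Say that it is weaker than the joint test for non-monotone patterns or an effect confined to one extreme band, and that it does not override the joint test.
4. Show the transfusion odds ratio in every band with its 95% CI, as description, whatever the result of the test.

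The cost is a few sentences, one additional model per outcome and one table. No new data are needed. The joint test comes from the model already planned, and the trend is secondary, so the 5% level of the deciding test is unaffected.

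### Effect modification, one of the two objectives, is reported only if p<0.05 and is planned only for mortality; no adjusted transfusion effect at each haemoglobin level is promised

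*Protocol*

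**What the plan says.** Section 3 sets two objectives. The first asks: "Is there an association between in-hospital mortality, 30-day mortality, and hospital length of stay and red blood cell transfusion at various levels of nadir haemoglobin". The second asks whether haemoglobin level and transfusion modify each other's effect on the same three outcomes: in-hospital mortality, 30-day mortality and length of stay.

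Section 6.2 divides haemoglobin into seven categories: "below 50 g/L, 50-59 g/L, 60-69 g/L, 70-79 g/L, 80-89 g/L, 90-99 g/L, 100 g/L or over".

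Section 6.4 plans logistic regression for the two mortality outcomes. For the third it says: "A zero-truncated negative binomial regression model will be applied to the length of stay outcome". The paragraph on effect modification opens by naming all three outcomes, but the analysis it then gives is that "an interaction term between nadir haemoglobin level and red blood cell transfusion will be added to the multivariable logistic regression models". It closes with the reporting rule: "Only significant interactions (defined as p-values <0.05) will be reported, with calculated odds ratios for interaction terms presented".

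The last paragraph of section 6.4 adds Kaplan-Meier curves and Cox models of time to death, transfused against untransfused, by haemoglobin level. No p-value condition is attached to these.

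**The concern.** A non-significant interaction, shown with its intervals, is an answer to objective 2. The protocol itself treats one that way: section 5 (Literature Review) cites a vascular-surgery study's null interaction as evidence that transfusion acted alike at all haemoglobin levels. Under the rule in section 6.4, this study's own null result would not appear. Readers could not tell a similar effect at every level from too few patients to say.

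The rule also distorts what does appear, because an estimate shown only when it passes p<0.05 is on average too large in absolute size.

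The same paragraph leaves two further gaps. Length of stay is in objective 2 but has no stated interaction analysis. And objective 1 concerns "red blood cell transfusion at various levels of nadir haemoglobin", while the only by-level regression output named is the interaction odds ratio, which measures something else.

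Section 4 (Benefits) says the results may guide which thresholds future randomised trials choose, and stresses the lower haemoglobin levels. Data are likely to be thinnest there, so selective reporting would matter most.

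**Working it through.** The protocol gives no power, effect size, event rate or number of patients per haemoglobin level. Section 6.5 gives only an expected 60,000 to 70,000 admissions. There is therefore no figure of the plan's own to reproduce, and steps 3 to 5 are illustrations.

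**1. What the interaction odds ratio estimates.** Let b be the transfusion log odds ratio in the reference level, and g_k the product term for level k.
- Without product terms there is a single b, so one common odds ratio for all levels. Section 6.4 speaks of adding the interaction, so the base model does not contain it.
- With product terms, the transfused-versus-untransfused odds ratio in level k is exp(b + g_k).
- The interaction odds ratio is exp(g_k): the odds ratio in level k divided by that in the reference level.
- The interval for exp(b + g_k) needs Var(b) + Var(g_k) + 2Cov(b, g_k). A reader given only exp(g_k) and its interval cannot rebuild it.

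**2. Which outcomes are covered.**

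| Outcome | In objectives 1 and 2 | Interaction model stated | By-level output free of the p-value rule |
|---|---|---|---|
| In-hospital mortality | yes | yes, logistic | none named as an odds ratio |
| 30-day mortality | yes | yes, logistic | none named as an odds ratio |
| Length of stay | yes | no | none |
| Time to death | not named | not stated | Kaplan-Meier and Cox, to be plotted |

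The length-of-stay model also does not yield odds ratios, so the reporting sentence could not be applied to it as worded.

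**3. False positives.** Seven categories give 7 − 1 = 6 product terms per outcome. The chance of at least one p<0.05 when no interaction exists is:
- each term tested, independent: 1 − 0.95^6 = 0.265;
- each term tested, assumed pairwise correlation 0.5: about 0.21; 0.8: about 0.14;
- one joint test per outcome: 0.05.

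The terms share a reference level and so are correlated. The 26% is an upper figure within this range.

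**4. Exaggeration from the filter.** Let the estimate divided by its standard error be normal with mean d and variance 1, shown only if |z| > 1.96. The exaggeration is E(|z| given |z| > 1.96)/d, on the log scale.

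| True interaction (d, in standard errors) | Chance of being reported | Average exaggeration |
|---|---|---|
| 1 | 17% | 2.5-fold |
| 2 | 52% | 1.4-fold |
| 2.8 | 80% | 1.1-fold |

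**5. What could be hidden (cell sizes assumed, not in the protocol).** Take a reference level with 1,000 transfused and 40,000 untransfused at 1% mortality. Its variance contribution is 1/(1,000 × 0.01 × 0.99) + 1/(40,000 × 0.01 × 0.99) = 0.101 + 0.003 = 0.104.
- Sparse level, 50 and 50 at 10% mortality: 2/(50 × 0.10 × 0.90) = 0.444. The standard error is √(0.444 + 0.104) = 0.74. The smallest ratio of odds ratios reaching p<0.05 is exp(1.96 × 0.74) ≈ 4.3. A true ratio of 2 is reported about 16% of the time.
- Fuller level, 1,000 and 3,000 at 3% mortality: 0.034 + 0.011 = 0.046 before rounding of the parts. The standard error is √(0.046 + 0.104) = 0.39. The smallest reportable ratio is about 2.1. A true ratio of 2 is reported about 43% of the time.

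**The case against.** The strongest case on the other side has four parts.

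**By-level information does exist.** A reader might infer that objective 1 gets no estimate at all by haemoglobin level. The document does not support that: the Kaplan-Meier and Cox analyses are by level and unconditional. This part stands. What remains is narrower. The Cox models are only to be plotted, no level-specific hazard ratio is promised, and time to death is none of the three named outcomes.

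**The sentence does not exclude other output.** A reader might take it to mean that interaction odds ratios are all that will be shown. The restriction is on which interactions are reported; the text does not say that nothing else will accompany them. This too stands. The regression text simply commits to nothing more.

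**The test may be a joint one.** The protocol speaks of adding an interaction term in the singular, so the 0.05 limit may apply to one test per outcome. A reader might conclude that the plan carries a 26% false-positive chance, or 1 − 0.95^12 = 46% over both mortality outcomes. Neither can be attributed to the plan, since it does not say how the limit is applied. The 46% also treats two heavily overlapping mortality outcomes as independent.

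**Detail belongs in the analysis plan.** Tables of estimates are commonly left there, and the study is retrospective, so fuller reporting would remain possible later. That is fair for table layout. It does not excuse the reporting rule, which is an explicit restriction that a later plan could lift only by contradicting the protocol.

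**Conclusion.** The point holds in this form. Followed as written, section 6.4 reports objective 2 selectively. It also leaves length of stay out of the interaction analysis, against section 3 and the opening of its own paragraph. And its regression text commits to no adjusted transfusion effect within each haemoglobin level for the three outcomes of objective 1. These conclusions rest on the wording alone.

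The sizes are conditional. The false-positive chance is 5% per outcome with a joint test. Term by term it is about 14% to 26%, depending on the correlation between terms. Exaggeration runs from about 1.1-fold at 80% power to 2.5-fold at 17% power, and the protocol gives no basis for placing the study in that range. The cell sizes in the last step of the working are assumptions that show only that a doubling of the odds ratio could go unreported.

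**What to change.** Replace the reporting sentence in section 6.4 with:

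> For all three outcomes the haemoglobin-level by transfusion interaction will be fitted (including in the length-of-stay model) and reported whatever its p-value: one joint cluster-robust Wald test (6 df), and the adjusted transfused-versus-untransfused effect with 95% CI within each haemoglobin level (odds ratio for mortality, ratio from the zero-truncated negative binomial model for length of stay).

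The preceding sentence, which adds the interaction to the logistic models only, should be widened to match. The cluster-robust form follows the variance adjustment for repeat admissions that section 6.4 already plans.

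The cost is one added term in the length-of-stay model and one table. Intervals in the lowest haemoglobin levels may be wide; showing that is part of answering the question.

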A recent systematic review and meta-analysis published in the Cochrane Library concluded there is no difference in morbidity or mortality between restrictive and liberal transfusion strategies. However, these trials are often confounded by transfusions administered pre-randomization, a lack of comparable transfusion dosing regimens between studies, and at times small differences in actual mean pre-transfusion haemoglobin levels between control and intervention arms. In addition, these randomized controlled trials still leave many important questions unanswered. For example, are haemoglobin thresholds lower than 70 g/L just as effective as haemoglobin levels higher than 70 g/L? Some have suggested lower haemoglobin thresholds may be just as effective. Interestingly, lower thresholds are already applied in clinical practice in challenging patient populations.

Other studies have investigated mortality in patients with very low haemoglobin levels who do not receive red blood cell transfusions. These studies found that each 10 g/L decrease in haemoglobin below 80 g/L was associated with a 1.8 to 2.5 times increased odds of mortality, with sharper increases in mortality observed when the haemoglobin fell below 50 g/L. However, these studies do not address what effect red blood cell transfusion would have on outcomes at various nadir or pre-transfusion haemoglobin levels.

Additionally, while many studies have investigated the effect of anaemia on outcomes independent of red blood cell transfusion, and the effect of red blood cell transfusion on outcomes independent of anaemia, very few investigate if and how these two independent risk factors interact with each other.

The aim of this study is to determine what relationship red blood cell transfusion has with mortality and length of stay at various levels of nadir haemoglobin. To achieve this objective a retrospective observational study will be conducted, involving three hospitals from Western Australia. The study will include all elective and emergency surgical admissions over a 9 year period (July 2008 – June 2017).

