Some observational studies in the surgical setting have sought to address this gap in the literature by comparing outcomes between patients transfused and those not transfused across various levels of anaemia. For example, in patients undergoing cardiac surgery, Shaw and colleagues used a propensity-matched analysis to compare the outcomes of patients transfused to those not transfused at four preoperative haematocrit levels (a measure of anaemia). They found that transfused patients had higher mortality rates than those not transfused, at all levels of haematocrit. Kougais and colleagues studied the impact of postoperative nadir haemoglobin levels and transfusion on outcomes in patients presenting for elective operations for atherosclerotic vascular occlusive disease at one hospital. They found that neither red blood cell transfusion nor nadir haemoglobin level was associated with the composite end point of death and/or myocardial infarction. Interestingly, there was no significant interaction between transfusion and nadir haemoglobin, suggesting transfusion had the same effect on outcome regardless of the nadir haemoglobin level.

While these studies provide some insights into differences between outcomes in transfused and non-transfused anaemic patients they also leave many unanswered questions. For example, what are the outcomes in patients with haemoglobin thresholds lower than 70 g/L?

Two case series have investigated mortality in patients with very low haemoglobin levels who do not receive red blood cell transfusions. These studies found that each 10 g/L decrease in haemoglobin below 80 g/L was associated with a 1.8 to 2.5 times increased odds of mortality, with sharper increases in mortality observed when the haemoglobin fell below 50 g/L. However, these studies do not address what effect red blood cell transfusion would have on outcomes at various nadir haemoglobin levels.

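### For mortality, effect modification is measured on the odds-ratio scale alone, which does not show how the absolute association of transfusion with death varies across haemoglobin bands

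*Protocol*

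**What the plan says.** Objective 2 in Protocol section 3 asks: "Is there an effect modification between levels of nadir haemoglobin and presence of a red blood cell transfusion", for both mortality outcomes and for length of stay. It names no scale.

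Section 6.4 fixes the method: "an interaction term between nadir haemoglobin level and red blood cell transfusion will be added to the multivariable logistic regression models". It continues with "Only significant interactions (defined as p-values <0.05) will be reported", "with calculated odds ratios for interaction terms presented". No risk difference, standardised risk or other additive measure is mentioned for mortality.

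Section 6.4 also plans Kaplan-Meier curves and plotted Cox models comparing transfused with untransfused patients by haemoglobin level. Length of stay has a zero-truncated negative binomial model, so it is not on the odds-ratio scale.

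The haemoglobin bands in section 6.2 are "below 50 g/L, 50-59 g/L, 60-69 g/L, 70-79 g/L, 80-89 g/L, 90-99 g/L, 100 g/L or over". On how risk changes between bands, the Synopsis cites studies of untransfused patients in which "each 10 g/L decrease in haemoglobin below 80 g/L was associated with a 1.8 to 2.5 times increased odds of mortality", with a steeper rise below 50 g/L.

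**The concern.** Whether one factor modifies the effect of another depends on the scale. If baseline risk is similar in every band, odds ratios and risk differences tell much the same story. If it differs many-fold, they separate: a constant odds ratio means a growing risk difference, and a constant risk difference means a changing odds ratio.

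The protocol's own background points to the second situation. Section 4 says that the results may guide which transfusion thresholds are chosen for future randomised trials. For that use, a reader will want to know how mortality differs between transfused and untransfused patients, in absolute terms, at each level. A ratio of odds ratios does not give this by itself. A null result could accompany a several-fold change in the absolute association, and a significant one could accompany a constant absolute association.

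Reporting every interaction, significant or not, would not settle the matter, because the answer would still be on one scale.

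**Working it through.** The protocol states no figure for the interaction, so there is none to reproduce. The check asks how far the absolute association can vary when the odds-ratio interaction is exactly null.

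**Inputs from the protocol**
- Odds of death multiplied by g = 1.8 to 2.5 per 10 g/L fall below 80 g/L (Synopsis and Literature Review).
- Bands 10 g/L wide (section 6.2). From 70-79 g/L to below 50 g/L is k = 3 steps, so the odds rise by 1.8³ = 5.8 to 2.5³ = 15.6 times. The steeper rise reported below 50 g/L is left out.

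**Assumptions not in the protocol**
- Untransfused mortality at 70-79 g/L: p = 1%, 2% or 5%.
- Transfusion odds ratio, the same in every band: 0.67 or 1.5.
- The gradient, which comes from case series of untransfused patients, describes the untransfused patients of this cohort.

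**Formulas**
- Untransfused odds k steps down: o = p/(1 − p) × gᵏ. Untransfused risk: o/(1 + o).
- Transfused risk: (o × OR)/(1 + o × OR).
- Risk difference (RD): transfused risk minus untransfused risk.

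**Example**, p = 2%, g = 1.8, OR = 1.5. At 70-79 g/L the risks are 2.00% and 2.97%, RD +0.97 points. Below 50 g/L, o = 0.0204 × 5.832 = 0.119. The risks are 10.64% and 15.15%, RD +4.51 points. The ratio of the unrounded differences is 4.7.

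**All cases, odds-ratio interaction exactly 1**

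| p at 70-79 | g | OR | RD at 70-79 (points) | RD below 50 (points) | Ratio |
|---|---|---|---|---|---|
| 1% | 1.8 | 0.67 | −0.33 | −1.77 | 5.4 |
| 1% | 1.8 | 1.5 | +0.49 | +2.56 | 5.2 |
| 1% | 2.5 | 0.67 | −0.33 | −4.07 | 12.4 |
| 1% | 2.5 | 1.5 | +0.49 | +5.51 | 11.2 |
| 2% | 1.8 | 0.67 | −0.65 | −3.25 | 5.0 |
| 2% | 1.8 | 1.5 | +0.97 | +4.51 | 4.7 |
| 2% | 2.5 | 0.67 | −0.65 | −6.57 | 10.1 |
| 2% | 2.5 | 1.5 | +0.97 | +8.18 | 8.4 |
| 5% | 1.8 | 0.67 | −1.59 | −6.43 | 4.0 |
| 5% | 1.8 | 1.5 | +2.32 | +8.04 | 3.5 |
| 5% | 2.5 | 0.67 | −1.59 | −9.60 | 6.0 |
| 5% | 2.5 | 1.5 | +2.32 | +10.10 | 4.4 |

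The ratio runs from about 3.5 to about 12.

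**Converse.** With p = 2% and a constant difference of −1 point, the odds ratio is 0.49 at 70-79 g/L and 0.90 (g = 1.8) or 0.95 (g = 2.5) below 50 g/L. The odds-ratio scale then shows strong modification although the absolute difference is the same in every band.

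**The case against.** The strongest reply is that nothing here is wrong. A product term in a logistic model is a standard test of effect modification, Objective 2 names no scale, and section 6.4 contradicts no other part of the protocol. Standardised risks are post-estimation output that a statistical analysis plan could add. This stands in so far as no planned estimate or test is invalid. It does not remove the point, because section 6.4 does fix a test, a significance rule and an effect measure for mortality, all on one scale.

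A second reply is that absolute results are planned. The Kaplan-Meier curves show survival for transfused and untransfused patients in each band, so it would be too strong to say that the study looks at odds ratios alone. But no adjustment is stated for these curves, and neither they nor the Cox plots are given a contrast, an interval or a role in judging effect modification.

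Two stronger readings are tempting and are not supported:
- A reader might infer that the study will announce equal effects at all levels if the interaction is null. The Literature Review does gloss another group's null interaction as "suggesting transfusion had the same effect on outcome regardless of the nadir haemoglobin level", but that is a comment on a different study with a composite endpoint. Section 6.4 contains no such interpretation rule.
- A reader might treat a particular fold-change as implied by the protocol. It is not, since the protocol gives neither a baseline mortality nor a transfusion odds ratio.

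**Conclusion.** The point holds as a limitation of scale for the two mortality outcomes, with an inexpensive improvement available. It is not an error in the planned test. Under the stated assumptions (1% to 5% untransfused mortality at 70-79 g/L, a constant odds ratio of 0.67 or 1.5, and the cited gradient carried over to this cohort), a null odds-ratio interaction goes with an absolute association about 3.5 to 12 times larger below 50 g/L than at 70-79 g/L. The multiple moves with the inputs, but it stays well above 1 in every case computed.

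The planned interaction answers Objective 2 on one scale and leaves open how the absolute association varies with haemoglobin, which bears on the stated use in choosing thresholds to study. In this observational design, any such risk difference would be an adjusted association. It should not be read as deaths caused or prevented by transfusion.

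**What to change.** In section 6.4, keep the odds-ratio interaction and add the following for in-hospital and 30-day mortality:

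- From the same logistic models, with the interaction term retained whatever its p-value, report for each haemoglobin band the covariate-standardised mortality with and without transfusion.
- Give the difference between the two with a 95% interval that allows for repeat admissions of the same patient (for example, the delta method with the planned robust variance, or a bootstrap that resamples patients).
- State that any conclusion on effect modification names its scale, and that a null odds-ratio interaction is not read as the same absolute effect at all levels.
- Describe the differences as adjusted associations.

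The cost is a few lines of text and some post-estimation work on models already planned, with no new data. The intervals will be wide in the lowest bands if, as is likely, few patients fall there.
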